h = illicit opioid (e.g., heroin) drug screen or self-report is positivem = medication for opioid use disorder (MOUD) or self-report is positive

'-' = missing value

Cases measuring “abstinence without MOUD”:

Heroin use, no MOUD {1,1,1,h,h,1,1,1,1,1,h} = 9/12

Heroin use, no MOUD, missing weeks {1,1,1,h,h,1,--,1,1,--,} = 6/12

MOUD use, no Heroin {1,1,m,m,m,m,1,1,1,1,1} = 8/12

MOUD use, no Heroin, missing weeks {1,1,m,m,m,m,1,1,--,} = 4/12

[figure not shown]
Heroin use, MOUD use {1,1,h,h,h+m,m,m,m,m,h,1,1} = 4/12

Heroin use, MOUD use, missing weeks {1,1,h,h,h+m,m,--,m,h,--,} = 2/12

[figure not shown]
**Table 2.** Participant selection criteria

Inclusion Criteria	Exclusion Criteria


(1) Meet DSM-5 criteria for opioid use disorder (any severity level) alone or comorbid with stable medical diseases (except for certain medications below)

(2) Stated desire to be opioid abstinent without medication for opioid use disorder

(3) Initiating opioid discontinuation at study site

(4) In good general health as evidenced by medical history

(5) Male or female, aged 18-65 years

(6) Provision of signed and dated informed consent and HIPAA authorization form

(7) Stated willingness to comply with all study procedures and availability for the duration of the study (including inpatient stay and participation in video assessments and remote drug screens for the duration of the 12-week outpatient study period)

(8) Use of highly effective contraception for at least 1 month prior to screening and agreement to use such a method for the duration of the study

(9) treatment will not commence until the Clinical Opiate Withdrawal Scale total score is 13 or greater (at least moderate withdrawal); thus, a consented participant could be dis-enrolled

	

(1) Acute/unstable illness: conditions making it unsafe to participate

(2) Chronic illnesses: primarily seizures and dementing illnesses, including medications for these neurological conditions

(3) Current serious psychiatric disease: psychosis, bipolar disorder

(4) Current requirement to detoxify for alcohol or benzodiazepines

(5) Current use of anxiolytics, hypnotics (prescription and over-the-counter), antidepressants, anticonvulsants, sedating H1 antihistamines (non-sedating second generation H4 antihistamines are allowed), prescription and over-the-counter stimulants

(6) Current diagnosis other than opioid use disorder requiring chronic opioid treatment

(7) Presence of a cardiac pacemaker

(8) Pregnancy or lactation. Females who do not agree to sexual abstinence or are heterosexually active and not using (self-report) medically approved birth control measures (sterilization, tubal ligation, oral/depot contraceptives, abstinence, intrauterine device, barrier method such as condom/foam, or a cervical cap combined with a spermicide), are not eligible

(9) Receiving extended-release buprenorphine within 300 days of enrollment

**Figure 1.** *Upper panels:* NET Device (left), mastoid-region electrode placement (middle), and cumulative distribution function of participants' device utilization (percentage of sample with device "on") across hours in two pilot studies conducted in Kentucky and Scotland (right). *Lower panels:* Time course of device intensity setting (left), and cumulative distribution functions of scores for the Subjective Opioid Withdrawal Scale (SOWS; middle) and craving (right).

**Figure 2.** Study schema

Notes: “NET”, NeuroElectric Therapy. “COWS”, Clinical Opiate Withdrawal Scale. “TLFB”, Timeline Followback.

**Figure 3. Schedule of Activities**

Schedule of Activities (SoA)	Pre-Screening	Screening	Inpatient					Outpatient	
			Week -1	Week 1			Weeks 2-3	Week 4	Weeks 5-15 Week 16
Inpatient Study Day(s)		Day 1	Day 1, Baseline	Day 1, One Hour Elapsed	Days 2-7	Day 14 Day 21	Day 28 (Discharge from Site)		
Outpatient Test Weeks								OP Wk 1-11 each Day 7	OP Wk 12 Day 7
Study Site Admission		X							
Study Site Discharge							X		
End of Study									X
Informed Consent	X	X 							
Demographics		X							
Medical and Psychiatric History		MIA 							
Drug Use History		MIA 							
Physical Exam (including height and weight)		MIA 							
Vital Signs (BP, HR, RR, O2)		MIA 							
Drug Screen		MIA 					X	X	X
Contraception, Pregnancy Test, Menstrual Cycle	X						X	X	X
Drug Use Timeline Followback Interview (TLFB)								X	X
Eligibility (Inclusion/Exclusion)	X								
Contact Data	X						X		
Randomization and Stratification	X								
COWS			X 	X	X				
Administer Active/Sham Treatment (self-administration [sa])			X	sa	sa				
Opioid Craving Scale (OCS)			X	X	X	X	X	X	X
Treatment Perception (while device in use [sa])				X	sa				
Device Satisfaction Scale (while device in use [sa])				X	sa				
Device Tolerability (while device in use [sa])				X	sa				
Dass21: Depression, Anxiety and Stress			X				X		X
PANAS-SF: Positive and Negative Affect Scale (Short Form)			X	X	X				
Epworth Sleepiness Scale			X				X		X
Concomitant Medications				X	X	X	X	X	X
Adverse Events			X	X	X	X	X	X	X
Device Deficiencies				X	sa				
SF-12 Health Related Quality of Life (Short Form)							X		X

This drug screen is wider ranging to collect stratification information

Must be >13 for inclusion on Day 1

Paper (non-electronic) source data

"MIA" is Study Site Medical Intake Assessment

Notes: "OP", outpatient. "Wk", week. "sa", self-administered. "BP", blood pressure. "COWS", Clinical Opiate Withdrawal Scale, "HR", heart rate. "RR", respiration rate. "O2", oxygen saturation.

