### ***Randomization and blinding***

The biostatistician block-randomizes assignment of the ITT population to treatment (sham vs. active) using a 1:1 allocation ratio and, within each treatment group, stratification by sex (male/female) and non-opioid substance use disorder (presence/absence). The master codebook for randomization is kept in a secure location at Wayne State University and only the biostatistician and a research assistant (backup person) can access it.

Sham treatment, which controls for placebo effects, is designed to minimize sham recognition by the sponsor, principal investigator, participants, research assistants and treatment staff (i.e. quintuple blinding). Participants in the active arm receive standard NET treatment. Participants in the sham arm receive the same standard NET treatment as the active arm but will receive no electrical stimulation (cable is disabled beforehand). Sham credibility is evaluated for both arms based on surveys following the 1-hr treatment phase, and daily during device use. A single ‘treatment perception’ question asks: “How confident are you that you are receiving the real device treatment and not the placebo (sham) treatment?” Three ‘device satisfaction’ questions ask: (1) “How satisfied are you with the NET Device?” (2) “How willing are you to use the NET Model 901 Device?” and (3) “How willing are you to recommend the NET Model 901 Device to other people undergoing opioid discontinuation?”

Active and sham arms will receive identical device care and use instructions, identical equipment, attachment methods and locations, and identical daily reviews of device operation, electrode attachment, and withdrawal severity. The treatment apparatus presents both active- and sham-assigned participants with visual cues from the device’s “heartbeat” indicator (a blinking green light-emitting diode which indicates the device is active) during treatment. Research staff instruct each participant that the equipment is designed to be self-administered, that s/he can set the level of stimulation wherever it is comfortable, that stimulation is not always (and does not need to be) sensate, and that device use may be discontinued when s/he feels it is providing no benefit.

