### ***Outcome measures***

During the 12-week outpatient period, participants will be interviewed for safety and efficacy endpoints and undergo a remote drug screen. Remote interviews reduce risk of COVID-19 exposure for the participant and research assistant, and decrease transportation barriers (increased feasibility). Each week, the research assistant hosts a live video call with the participant, and conducts a timeline follow-back (TLFB) review of opioid, MOUD, stimulant, sedative, cannabis and alcohol use for each of the prior 7 days. At discharge from the inpatient facility, each participant will be given 12 kits (plus

one spare) of the Premier Biotech OralTox OT-80605, an FDA 510(K) cleared 6-panel rapid oral fluid drug screen. Each test covers amphetamines and methamphetamine (positive cutoffs = 50 ng/ml), opioids and THC (positive cutoffs = 40 ng/ml), oxycodone and cocaine (positive cutoffs = 20 ng/ml). Each individually packaged test is sealed in foil and is marked with a lot number and expiration date. Each individual test contains a QR code that encodes a unique identification number that will be used to validate authenticity and uniqueness of the screen. The participant receives printed and verbal instructions for use from the research assistant, is observed during each test, and test results with authenticating QR code are captured as an image file by the research assistant and saved for validation. In order to conduct this FDA-qualifying study during the COVID-19 pandemic, remote test methods were evaluated for use during the outpatient phase. When this study began, FDA had only approved a limited selection of oral fluid rapid tests for use in research. The authors selected TLFB self-report as the primary source for data, supplemented by such relevant oral fluid tests as were FDA approved.

The primary efficacy endpoint is each participant's overall percentage of weekly abstinence from illicit opioid use without use of MOUD. This is defined as the percentage of each participant's negative oral fluid samples and self-reports of illicit opioid, methadone, buprenorphine, and naltrexone use per week throughout the 12-week outpatient study period. The rationale for choosing this endpoint is to perform a rigorous test of the isolated efficacy of NET, with the safety net of allowing (and measuring) participants' use of MOUDs.

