During a given week, oral fluid samples and self/pharmacy reports that both indicate no illicit opioid, methadone, buprenorphine, or naltrexone use will be considered "opioid-abstinence without MOUD". Cumulative distribution function, time (days) to first use of illicit opioids, time (days) to first use of MOUD, and duration (weeks) of continuous abstinence without MOUD will be evaluated as supportive outcomes. Response profiles for each treatment arm are based on each participant's individual rates of weekly illicit opioid or MOUD use, including negative oral fluid results and daily

self (TLFB) of illicit opioid or MOUD use/non-use. **Table 1** presents explanatory cases of the primary efficacy endpoint measurement. The null hypothesis is that “opioid abstinence without MOUD” will not significantly differ between active and sham groups, whereas the alternative hypothesis is that “opioid abstinence without MOUD” will be superior in the active (relative to sham) treatment arm.

The secondary efficacy endpoint is each participant’s percentage of non-opioid drug-free weeks during the 12-week outpatient period. Non-opioids assessed include cocaine, sedatives, and stimulants. Use of alcohol and cannabis will be measured, but are not included in the secondary efficacy analysis, due to their legal status. Response profiles for each arm are based on each participant’s individual rates of weekly abstinence data, including negative oral fluid results and daily self-reports of non-opioid drug use/non-use (TLFB).

The secondary safety endpoint is the prevalence of all adverse events (AEs), serious adverse events (SAEs), adverse device effects (ADEs), serious adverse device effects (SADEs), unanticipated adverse device effects (UADEs), and device deficiencies.

Supportive and exploratory measures. Treatment retention will be measured throughout the inpatient and outpatient phases. Self-stimulation intensity (in 5-min bins), duration, and device on/off data from each NET Device are automatically transmitted to a computer server and processed offline. Opioid withdrawal symptoms, craving severity, and positive/negative affect are measured daily during the first inpatient week. Measures of depression, anxiety and stress, sleepiness, and health-related quality of life are obtained at the conclusion of inpatient and outpatient phases.

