### ***Participant selection criteria***

Screening includes informed consent, HIPAA authorization, assessment of demographics, contact data, pregnancy testing, contraception methods, medical history, and urine drug testing (including fentanyl, buprenorphine, and methadone). Assessments are aligned with the treatment

facility's standard of care such that electronic case report forms (eCRFs) can be rapidly reviewed for study eligibility by the remote investigator, given the time-sensitive nature of enrollment.

During the recruitment and informed consent process, participants are repeatedly told they can receive FDA-approved MOUD at the treatment facility instead of participating in the study. They are also told that upon discontinuation of device stimulation, and/or if they drop out of the study, they can receive TAU (including MOUD) at any time. All participants are given a "loss-of-opioid tolerance" warning (i.e. stopping opioids leads to reduced tolerance, and subsequent opioid use increases their risk of overdose and death), which they must sign. Participants are also given a naloxone kit upon discharge from the treatment facility and educated on its use. All of these procedures are documented in the medical record and case report forms.

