Secondary endpoint analyses are not powered, but may be used to demonstrate additional benefits of the treatment, provided it has been demonstrated that the primary endpoint shows clear statistical significance, as well as clinical meaningful benefits of the treatment [19]. Analysis of the secondary endpoint resembles primary endpoint analysis, using mixed-effect model testing for the between-group main effect.

Given that participants can control the level of device stimulation, exploratory regression analyses will seek to identify potential relationships between device utilization (e.g. number of minutes device ‘on’ [non-zero intensity], average intensity while device ‘on’) and efficacy endpoints.

Expected outcomes. We selected a single primary outcome (abstinence without MOUD). From our past experience at this same treatment facility, the expected group means for sham and NET arms are 0.48 and 3.97 weeks of average opioid abstinence with standard deviations 1.19 and 3.46, respectively. This results in effect size of 1.12. This effect size based on pilot data is rather large,

which is often the case due to limited scope of the pilot study. Thus, we took a conservative approach as suggested by Kraemer et al. [20] with moderate effect size of 0.45.

Safety endpoints. Secondary safety endpoints (AEs, SAEs, ADEs, SADEs, UADEs and device deficiencies) will be summarized using descriptive statistics.

Subgroup analysis. The analysis will stratify by sex (male/female) and non-opioid SUD (presence/absence). The expected outcome is that allocation on those variables will be balanced between the two groups. It is not anticipated that the primary outcome (opioid abstinence without MOUD) will differ across these subgroups. If significant baseline group imbalance is detected on any variable and its correlation with outcome ( $\geq 0.30$ ), that variable will be included as a covariate in the inferential analyses. If systematic variation is noted by any subgroups for primary or secondary outcomes, further exploration will be conducted via cluster analysis.

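### The secondary efficacy model has no term for pre-treatment cocaine, sedative or stimulant use, so participants without such use dilute the estimate and cost precision

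*Combined protocol and SAP*

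**What the plan says.** **Endpoint.** Under Outcome measures, the secondary efficacy endpoint is each participant's "percentage of non-opioid drug-free weeks during the 12-week outpatient period". The drugs counted are cocaine, sedatives and stimulants; alcohol and cannabis are recorded but left out. Nothing restricts it to people who used these drugs before treatment.

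**Follow-up measurement.** In each outpatient week the research assistant "conducts a timeline follow-back (TLFB) review of opioid, MOUD, stimulant, sedative, cannabis and alcohol use for each of the prior 7 days". In Figure 3 the row "Drug Use Timeline Followback Interview (TLFB" is marked only in the two outpatient columns.

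**Pre-treatment information.** Figure 3 also schedules "Drug Use History" and a drug screen within the site's medical intake assessment, both on paper. Footnote 1 says of the screen: "This drug screen is wider ranging to collect stratification information". Participant selection criteria adds "urine drug testing (including fentanyl, buprenorphine, and methadone". Randomization and blinding specifies "stratification by sex (male/female) and non-opioid substance use disorder (presence/absence".

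**Analysis.** The model under Efficacy endpoints names treatment, random effects and one covariate, length of inpatient stay. For the secondary endpoint: "Analysis of the secondary endpoint resembles primary endpoint analysis, using mixed-effect model testing for the between-group main effect". The Subgroup analysis paragraph says the analysis will be stratified by sex and non-opioid SUD. It adds a covariate only if that variable shows significant baseline imbalance and correlates at least 0.30 with outcome. The plan also states that secondary analyses are unpowered and usable only after a clear primary result.

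**The concern.** Eligibility requires opioid use disorder only, and stratifying on presence or absence of non-opioid SUD shows that the plan expects participants without one. A participant with no prior use of the three drug classes, who stays drug-free and attends every week, scores 12/12 under active or sham. The endpoint therefore mixes people who stopped with people who had nothing to stop.

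This has two effects on the overall comparison. The mean difference shrinks towards zero relative to the difference among prior users. In addition, the gap between non-users near 100% and users well below it enters the residual variance unless the model has a term for it. The second loss can be avoided with data the trial already collects. At stake is whether the only secondary efficacy endpoint can support the additional-benefit claim it is meant for.

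**Working it through.** **1. Is prior use in the model?** Four places were compared.
- *Efficacy endpoints:* one covariate, length of inpatient stay.
- *Secondary analysis:* resembles the primary, with no further term named.
- *Subgroup analysis:* stratification by SUD is mentioned, but not tied to the main-effect model.
- *Imbalance rule:* needs significant imbalance. Randomisation is stratified on SUD, so imbalance on that factor is unlikely and the rule would rarely bring it in.

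The answer is no, or at best not clearly.

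**2. Does the stratum match the endpoint?** Only in part. It is a yes/no diagnosis, not a measure of use. As worded it could include alcohol or cannabis disorder, which the endpoint excludes.

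**3. How large could the effect be?** The plan gives no figure to reproduce: no share of non-users, no secondary effect size and no alpha. What follows is an illustration.

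Inputs:
- n = 50 per arm (Study design).
- Assumed: two-sided 5% alpha; drug-free weeks among users m = 0.40 (sham) and 0.55 (active), so δ = 0.15; SD = 0.333, so d = 0.45. That d equals the primary endpoint's planning effect and is borrowed only as a reference.
- Assumed: a share q of non-users, all scoring 1.0 in both arms.

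Formulas:
- Overall difference = (1 − q)·δ
- Unadjusted variance per arm = (1 − q)·SD² + q(1 − q)(1 − m)², averaged over arms
- Residual variance with a prior-use term = (1 − q)·SD² + q(1 − q)·δ²/4
- Power = Φ(d·√(n/2) − 1.96)

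At q = 30%:
- Difference = 0.7 × 0.15 = 0.105.
- Unadjusted variances: sham 0.0778 + 0.21 × 0.36 = 0.1534; active 0.0778 + 0.21 × 0.2025 = 0.1203. Pooled SD = 0.370, d = 0.105/0.370 = 0.28, power 29%.
- With a prior-use term: 0.0778 + 0.21 × 0.0225/4 = 0.0790. SD = 0.281, d = 0.37, power 46%. The standard error falls by 1 − 0.281/0.370 = 24%.
- Users only: 35 per arm at d = 0.45, power 47%.

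| q | Overall difference (points) | Power, unadjusted | Power, prior-use term | Power, users only |
|---|---|---|---|---|
| 0% | 15.0 | 61% | 61% | 61% |
| 10% | 13.5 | 48% | 57% | 57% |
| 20% | 12.0 | 37% | 52% | 52% |
| 30% | 10.5 | 29% | 46% | 47% |
| 40% | 9.0 | 23% | 41% | 41% |
| 50% | 7.5 | 18% | 35% | 36% |

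A model term recovers precision but leaves the overall difference diluted. Only an estimate among prior users shows the difference on the users' scale.

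**4. What might a finer baseline measure add?** For a baseline–outcome correlation ρ, adjustment multiplies the standard error by √(1 − ρ²): 0.954 at ρ = 0.3 and 0.800 at ρ = 0.6, a cut of 5% to 20%. These correlations are assumptions too. The gain beyond the SUD stratum and intake data would be smaller.

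**The case against.** **Baseline information exists.** A reader might infer that the trial has no baseline drug-use data. It does: an intake drug history, a wider intake screen, urine testing and the SUD stratum. What is missing is a pre-treatment TLFB on the endpoint's scale and a stated use of the intake data in the secondary model. The intake form is not shown, so one cannot say that it lacks days or weeks of use.

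**The endpoint needs no baseline value.** This is correct. It is a post-discharge percentage, not a change score, and the overall difference is a legitimate average over everyone enrolled. The point concerns precision and interpretation, not validity.

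**Non-users are not automatic successes.** Also correct. Someone without prior use may start after stopping opioids, and the endpoint counts that. Missing weeks probably count against them as well: the Missing data paragraph says the secondary definition covers missing values, although it states the imputed value only for the primary. Both make the real gain from adjustment smaller than in the table.

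**The plan already stratifies by SUD.** This stands only partly. The sentence is under Subgroup analysis, and the described model omits the factor.

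**The endpoint is unpowered and depends on a primary success.** True, and it keeps the point minor. Even the users-only analysis reaches only 36% to 57% power in the illustration for q of 10% to 50%.

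**Conclusion.** The point holds as a modest loss of precision on the secondary endpoint. The endpoint includes participants without prior use, and the described model has no term for it. The overall difference is (1 − q) times that among users if non-users score 100% in both arms. The power figures rest on assumed rates and a borrowed effect size, so they show a possible range and do not estimate this trial's power.

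Two stronger readings are not supported. First, a reader might infer that non-users favour the active arm. Randomisation is 1:1 and stratified on non-opioid SUD, so non-users are expected in equal proportion in both arms; the effect is dilution, not bias. Second, a reader might extend the point to the primary endpoint. All participants have opioid use disorder and must reach at least moderate withdrawal before device use. Pre-admission weeks abstinent without medication for opioid use disorder would thus be near zero for almost everyone and could explain little variance.

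**What to change.** Before unblinding:
1. Name the non-opioid SUD stratum as a term in the secondary model.
2. Add an indicator of any pre-treatment cocaine, sedative or stimulant use, taken from the intake drug history and wider intake screen. Fix the coding rule without knowledge of treatment arm.
3. Prespecify a supportive estimate of the secondary endpoint among participants with such use at intake.
4. Show any expected power gain only as a range, with the assumed share of non-users and baseline–outcome correlation stated.

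Optionally, for future participants, add one TLFB on pre-admission use with the drug classes of the weekly interview. It should be completed before randomisation, or at the latest before device start. An interview on inpatient Days 2–7 would follow randomisation and device exposure, so treatment could influence both the covariate and who counts as a prior user.

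The cost is transcription of paper intake data, one or two model terms and, if the TLFB is added, one short interview per participant in a time-sensitive enrolment window. The primary model needs no change on this account.
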